1. SUMMARY

Rationale

The worldwide practice of fluid and vasopressor therapy in critically ill invasively ventilated patients is uncertain. Indeed, it is unclear whether there is a difference in fluid and vasopressor therapy in these patients between Low- and Middle-income Countries (LMICs) and High-income Countries (HICs).

Objective

To determine various aspects of fluid and vasopressor therapy in critically ill invasively ventilated patients in LMICs and HICs.

Hypothesis

There is substantial worldwide variation in practice of fluid and vasopressor therapy in critically ill invasively ventilated patients.

Study design

International, multicenter, observational study in critically ill invasively ventilated patients; data are captured during a predefined period per geographic region or country.

Study population

Critically ill invasively ventilated patients.

Main study parameter/endpoint

The primary outcome is a composite of various aspects of fluid therapy, including total volumes of types of fluids administered in the first three days after start of invasive ventilation and total volume of fluids infused in the first seven days after start of invasive ventilation. Secondary outcomes include timing of start, type, and duration of continuous administration of vasopressors; timing of start, infusion time and types of administered diuretics; daily urine output and cumulative fluid balances; and typical ICU outcomes, like duration of ventilation, lengths of stay in ICU and hospital, and mortality in the ICU and hospital, and at day-28, -60 and -90.

Nature and extent of the burden and risks associated with participation, benefit and group relatedness

Because of the observational design of the study using routinely collected data, there is no additional burden for the patient. Collection of data from ICU charts or electronic medical records systems is of no risk to the patients.

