6.1.2. Secondary study parameters

- Time of start of vasopressors;
- Route of administration for vasopressors (i.e. central vs. peripheral route);
- Types of vasopressor used;
- Daily urine output;
- Cumulative fluid balance;
- Timing of start, type and infusion time (i.e. bolus vs. continuous infusion) of administered diuretic;
- Incidence of atrial arrhythmias;
- Incidence of acute respiratory distress syndrome (ARDS)
- Incidence of renal replacement therapy;
- Incidence of persistent renal dysfunction, defined as the need for renal replacement therapy at ICU discharge;
- ICU length of stay, defined as the time between ICU admission and discharge or death;
- Hospital length of stay, defined as the time between hospital admission and discharge or death;
- Duration of ventilation, defined as the time between initiation of invasive ventilation and successful liberation of ventilation.
- Ventilator-free days and alive at day 28, defined as 28 - x if successfully liberated from ventilation x days after initiation. If subject dies within 28 days ventilator-free days is set to 0;
- All-cause ICU mortality, defined as any death during ICU stay;
- All-cause in-hospital mortality at day 28, defined as any death during hospital stay before or on study day 28;
- All-cause in-hospital mortality at day 60, defined as any death during hospital stay before or on study day 60;
- All-cause in-hospital mortality at day 90, defined as any death during hospital stay before or on study day 90;

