6.2. Study procedures

Patients in participating centers are screened on a daily basis. Eligible patients are included during the 28–day observation period, from Monday at 8:00 AM to the Monday four weeks later at 7:59 AM (in time zones of the participating centers). The timing of the 28–day observation period will be flexible for participating centers and determined at a later stage together with the international study–coordinator and each national investigator. Times points of data collection:

- Demographic and baseline data are collected from the clinical files – at ICU admission;
- Types, quantities, of administered fluids– during the first three calendar days with high-granularity. From day 4-7 lower granularity data concerning the total volume of infused fluids will be collected;
- Types and modalities of administration of vasopressors – over a maximum of seven days of ICU admission;
- Vital signs, laboratory results and limited treatment parameters are collected – once daily for a maximum of seven days;
- Cumulative fluid balance – calculated once a day on a time point convenient per each center for a maximum of seven days; and
- Outcomes – recorded at 90 days, the day of death or hospital discharge, whichever comes first.

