6.2.4. Follow-up

Participants are subject to follow-up until hospital discharge, day 90 or death.

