8.2. Plan of analysis

Subjects that are transferred to another ICU in the first three calendar days of ICU admission will be excluded from analysis. Subjects that are transferred to another ICU after the first three calendar days, but before seven days are excluded from analysis of the secondary endpoints. Patients admitted due to pancreatitis, burns, diabetic ketoacidosis, severe rhabdomyolysis and sub-arachnoid bleeding will be analyzed separately and excluded from analysis if less than 30 subjects are included in each category. Subjects diagnosed with sepsis or ARDS during the first three calendar days of ICU admission will be part of a subgroup analysis. Associations with outcomes will be assessed through regression modelling. Time to event variables are analyzed using Cox regression and visualized by Kaplan–Meier plots. For each analysis proposed, a complete statistical analysis plan will be prepared, finalized and made available before starting the analyses. Statistical analyses are conducted using R (www.r-project.org). A *P*–value of less than 0.05 is considered statistically significant.

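### Kaplan–Meier curves for liberation, and for in-hospital death if plotted over time, overstate absolute risk when the competing event is censored; section 8.2 should name cumulative incidence instead

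*Protocol*

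**What the plan says.** Section 8.2 gives one rule for every time-to-event outcome: "Time to event variables are analyzed using Cox regression and visualized by Kaplan–Meier plots". It does not list those outcomes, say how deaths or live discharges are censored, or mention competing events. The same section promises a complete statistical analysis plan for each analysis.

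Section 6.2.4 fixes the end of observation: "Participants are subject to follow-up until hospital discharge, day 90 or death". Section 6.2 agrees, with outcomes "recorded at 90 days, the day of death or hospital discharge, whichever comes first".

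The endpoint definitions in section 6.1.2 treat death differently:

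- Ventilation: "Duration of ventilation, defined as the time between initiation of invasive ventilation and successful liberation of ventilation". Death is not mentioned.
- Mortality (day 90; days 28 and 60 have the same form): "All-cause in-hospital mortality at day 90, defined as any death during hospital stay before or on study day 90".
- Stay: "ICU length of stay, defined as the time between ICU admission and discharge or death" and "Hospital length of stay, defined as the time between hospital admission and discharge or death". Death is one of the two ways a stay ends.
- Ventilator-free days: death within 28 days scores zero.

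The Summary labels the mortality outcomes more loosely: "mortality in the ICU and hospital, and at day-28, -60 and -90". Section 5.5 plans logistic regression for associations with mortality.

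**The concern.** Kaplan–Meier treats a censored patient as someone who can still have the event later, at the same rate as those who remain under observation. Two of the endpoints break that assumption if the competing event is censored.

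- **Liberation.** A patient who dies while ventilated will never be liberated. Censoring at death counts that patient as a future liberation.
- **In-hospital death.** A patient discharged alive can no longer die in hospital and is no longer followed. Discharge is the natural censoring date under section 6.2.4. Censoring there assigns the inpatient death rate to people well enough to leave.

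In both cases 1 minus the Kaplan–Meier estimate (1−KM) exceeds the proportion of patients who actually have the event. The protocol deals with this for ventilator-free days but not for duration of ventilation. At stake are the absolute probabilities read off the published curves.

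**Working it through.** **The plan's own figures.** Section 5.5 needs 150 events with 20% ARDS incidence and 30% mortality: 150 / (0.20 × 0.30) = 2500 patients. With 50 admissions per ICU, 25% of them ventilated beyond 24 hours: 2500 / (50 × 0.25) = 200 ICUs. Both reproduce. Neither depends on a Kaplan–Meier curve, so this point does not change them.

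**Inputs for the illustration.** The 30% is the mortality rate that section 5.5 gives for ARDS. Applying it to all ventilated patients is an assumption. The times to exit and the constant hazards are also assumptions; the protocol gives neither.

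**Formulas.** Let p be the share of exits that are the event of interest, and L the total exit hazard (1/mean, or ln 2/median).

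- True cumulative incidence: p × (1 − exp(−L t))
- 1−KM with the competing event censored: 1 − exp(−p L t)

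**Liberation by day 28**, with 30% dying ventilated and a median of 7 days to liberation or death. Here p = 0.7, and 28 days is four medians, so exp(−L t) = 0.5⁴ = 0.0625.

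- True: 0.7 × (1 − 0.0625) = 65.6%
- 1−KM: 1 − 0.5^(0.7 × 4) = 1 − 0.5^2.8 = 85.6%

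**In-hospital death**, with 30% dying and a mean of 20 days to discharge or death.

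| Day | True: 0.3 × (1 − exp(−t/20)) | 1−KM: 1 − exp(−0.3t/20) |
|---|---|---|
| 28 | 23% | 34% |
| 60 | 29% | 59% |
| 90 | 30% | 74% |

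**Range over the assumptions.**

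| Endpoint | Share dying | Median time to exit | True | 1−KM |
|---|---|---|---|---|
| Liberation, day 28 | 20–40% | 4–10 days | 51.4–79.4% | 68.8–97.9% |
| In-hospital death, day 28 | 20–40% | 7–21 days | 12.1–37.5% | 16.9–67.0% |
| In-hospital death, day 90 | 20–40% | 7–21 days | 19.0–40.0% | 44.8–97.2% |

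In every combination checked, 1−KM lies above the truth.

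**Where the problem disappears.** A simulation of 200,000 patients used 30% dying and a median exit of 14 days (a mean of about 20 days).

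- With live discharges kept in the risk set to day 90 as non-events, Kaplan–Meier gave 22.5%, 28.6% and 29.7% at days 28, 60 and 90. These equal the cumulative incidence.
- For length of stay as defined, ending at discharge or death, Kaplan–Meier and the empirical distribution both gave 75.0% by day 28. There is no competing-risk bias in that endpoint.

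**The case against.** The strongest reply is that the protocol never says in-hospital mortality will be drawn as a curve, nor that live discharges are censored. Section 6.1.2 defines mortality at days 28, 60 and 90 as status by a fixed day. Section 8.1 provides proportions and Fisher's exact test for such data, and section 5.5 plans logistic regression. None of these uses Kaplan–Meier. The reply stands: a reader might infer that the reported fixed-day mortality will be inflated, and the documents do not support that. The overstatement arises only if in-hospital death is plotted over time with live discharges censored. The 74% against 30% contrast depends on that unstated choice as well as on assumed stays.

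Three other inferences also go too far:

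- **That death biases the length-of-stay curves as a competing event.** Death is part of both definitions. An early death does count as a short stay, but that is a matter of interpretation.
- **That the Cox results are invalid.** A Cox model that censors the competing event estimates a cause-specific hazard ratio. That suits an association question, although it does not translate directly into a difference in risk.
- **That contrasts between income groups are shown to be distorted.** They could be if discharge timing differed between groups, but the documents give no figures from which to establish it.

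The last reply is that censoring rules and competing-risk estimators belong in the promised analysis plans. This answers only part of the point. The protocol does not leave the estimator open; it names Kaplan–Meier. An analysis plan that followed section 8.2 literally and censored deaths would carry the error into the liberation curves.

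**Conclusion.** The point holds in a limited form. Section 8.2 names an estimator that overstates the absolute probability of liberation if deaths are censored, and of in-hospital death if that is plotted with live discharges censored. Under the assumed constant hazards the illustrative excess is 20 percentage points for liberation by day 28 (85.6 − 65.6) and about 44 points for in-hospital death by day 90 (74 − 30). The direction was the same throughout the range checked. The size depends on exit times that the protocol does not give and on an ARDS mortality rate applied more widely.

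The effect is confined to plotted absolute risks. Hazard ratios, length of stay as defined, binary mortality, ventilator-free days, the logistic model, the descriptive primary outcome and the sample size are unaffected. It should be fixed, but it is not critical.

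**What to change.** In section 8.2, and in each analysis plan that follows from it:

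1. Replace the Kaplan–Meier plot for liberation with an Aalen–Johansen cumulative incidence curve, with death as the competing event.
2. If in-hospital death is shown over time, use the same method with discharge alive as the competing event, or state that live discharges stay at risk to day 90 as non-events.
3. Label the Cox results for these endpoints as cause-specific hazard ratios. Fine–Gray models are optional.

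Two optional additions are to report length of stay in survivors as well, and to change the Summary so that mortality at days 28, 60 and 90 is called in-hospital mortality, matching section 6.1.2.

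The cost is wording and minor analysis work. Section 6.2.3 already collects the date ventilation started (part A) and the dates of last extubation, death, and ICU and hospital discharge (part F). No new data are needed and the sample size does not change.

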9. ETHICAL CONSIDERATIONS

9.1. Regulation statement

The study will be conducted according to the principles of the Declaration of Helsinki as stated in the current version of Fortaleza, Brazil 2013. Data management, monitoring and reporting of the study will be performed in accordance with the International Conference on Harmonization – Good Clinical Practice (ICH–GCP) guidelines.

This project does not subject participants to an intervention. Also, this study does not require additional blood collection, or other diagnostic procedures.

9.2. Ethical and Regulatory authorities' approval

The study protocol is submitted to the IRB of the Amsterdam UMC for ethical review. All participating centers must submit the study protocol to the local Institutional Review Board for ethical judgment and obtain document of proof that the trial has been subject to Institutional Review Board/Institutional Ethical Committee (IRB/IEC) review. Considering that all study data is recorded from medical charts and no additional data collection or patient assessment is performed, ethical approval may not be required in some centers. However, where ethical approval is required, this approval must be obtained before the start of inclusion.

If authorization/approval/notification by the regulatory authorit(y)(ies) is applicable locally, this document should be obtained prior to initiation of the trial in compliance with the applicable regulatory requirement(s).

9.3. Patient information and informed consent

Only if applicable, informed consent forms and any other written information to be provided to the subjects as well as advertisement for subject recruitment (if used) should be subject to IRB/IEC review and given approval/favorable opinion. If informed consent is not required by the local IRB, a waiver must be obtained from the Institutional Review Board.

The study coordinator provides a template of Patient Information Sheet and Participant's Informed Consent and Authorized Informed Consent in English

10. ADMINISTRATIVE ASPECTS AND PUBLICATION

10.1. Handling and storage of data and documents

All patients will be identified with a study identification code. The codebook will be stored digitally and in paper. The paper version will be stored behind a lock and the digital form will be encrypted with a double password. All de-identified data will be stored for the length of the study and for 20 years afterwards, for further publication. The codebook will be kept for 5 years after the end of the inclusion period. The study will be registered at ClinicalTrials.gov.

10.2. Public disclosure and publication policy

The results of this service review will be published in a peer-reviewed medical journal. All participants in the project will get credit for the publication. National coordinators and all local investigators will be granted collaborative authorship. After publication of the primary results, on request the pooled dataset will be available for all members of the PRoFLUID collaboration for secondary analysis, after judgment and approval of scientific quality and validity of the proposed analysis by the Steering Committee. Before submission the final version of all manuscripts related to the PRoFLUID dataset must be approved by the Executive Steering Committee.

10.3. Organization

The role of the **International coordinator** is to centrally manage common scientific and administrative aspects related to the project. He will assist National coordinators in all phases of project start-up, ethical approvals submissions, patient inclusion and data monitoring. He will have direct administrator access to the web-based data management software and assist national and local coordinators in ensuring data safety and quality.

National coordinators will be appointed in each participating country. They will identify and recruit local participating centers. They will assist and train the site coordinators and oversee the conduct of the study according to ICH-GCP guidelines. They will ensure that all local necessary ethical and regulatory approvals are obtained before start of patient inclusion. They will assist and validate translation of study documents (protocol, CRF, patient informed consent form) and help coordinating data cleaning in their countries if needed.

Local investigators in individual participating centers will provide scientific and structural leadership in their center. They will ensure all local necessary ethical and regulatory approvals are obtained before start of patient inclusion. They will train and

monitor their local research group, to ensure the study is conducted according to ICH–GCP guidelines. They guarantee the integrity of data collection and ensure timely completion of CRFs.

